9. STATISTICAL CONSIDERATIONS

9.1 General Design Issues

The primary objective of the study is to evaluate the effect of MBSR in improving asthma control. We hypothesize that asthma control as assessed by the Asthma Control Questionnaire³ will improve significantly more in MBSR than in HLC participants at 18 month follow-up.

Secondary objectives are to evaluate whether respiratory interoceptive accuracy (Breath Perception Discrimination Test) mediates any improvements in asthma control; whether MBSR affects asthma-related QoL, lung function (change from baseline in 2-week average morning peak expiratory flow (PEF) and spirometry (Forced Expiratory Volume in 1 second (FEV₁)); and the cost-effectiveness and cost-utility of participation in MBSR on clinical outcomes.

We are employing a randomized controlled trial as the most suitable design to test the hypotheses. The measures we will use, together with their reliability and validity are described in the table of measures contained in Section 6.

9.2 Sample Size and Randomization

The trial size was determined based on hypothesized intervention effects on ACQ score, the primary outcome. We will recruit 254 individuals, but base power calculations on n=216 (108 per arm) anticipating $\leq 15\%$ loss to follow-up. With one baseline measure and 3 follow-up measures at 6, 12 and 18 months, the trial can detect an intervention effect of 0.25 ACQ score improvement using ANCOVA (or linear mixed models) method at 5% significance level and at least 80% power. This treatment effect is consistent with recent reported drug-trials for asthma control. Based on literature, for sample size estimation we assumed the mean (SD) of ACQ scores for the MBSR and HLC groups are 1.24 (0.66) and 1.49 (0.66) averaged over the three follow-up time points, respectively, and a serial correlation of 0.45 within patients. We expect to recruit patients from 12 physicians at each site, with on average each physician contributing 9 patients. Because within physician correlation has not been reported in literature and our small-sized pilot study does not allow an accurate estimation, we conservatively assumed a modest within physician correlation of 0.05. The sample size was estimated using Stata MP 12.

Our sample size estimation and power analysis are conservative and the treatment effect is chosen for other important reasons: a) to preserve the possibility of addressing treatment heterogeneity by select patient and physician characteristics (e.g. differential effects between male and female participants, ethnicity); we plan to conduct subgroup analysis and examine how treatment effects may differ. Such analysis will be very important when refining the treatment protocols and for dissemination if proved effective; b) other than the primary outcome, we are also interested in other primary/secondary outcomes described below and powered the trial to detect meaningful changes in these outcomes as well. The sample size is determined to allow us to achieve all these analytic goals, not just for the primary outcome.

Randomization stratified by asthma severity and study site with each stratum in randomly allocated block sizes of two using the ralloc program in Stata^{82, 83} was determined most appropriate treatment assignment procedure as it will control for the majority of confounds including disease severity, location, prior conditions, race, gender etc. Procedures for the maintenance of trial randomization codes and maintaining appropriate masking for the study have been discussed in Section 6.2.3.

In total, the study will recruit 254 participants, 127 from each of the sites. The specific recruitment goals stratified by study site and asthma severity (mild, moderate or severe asthma) are: UMass Memorial Health Care (UMMHC): and the Miriam Hospital. Data is expected on 216 participants at study completion.

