Retention of Participants: We expect to retain 85% of participants at 18-months. Contact information will be collected from the participant at enrollment. Tracking procedures will be established and implemented for those not completing a scheduled study assessment, or who cannot be reached. Attempts to locate participants will be made by telephone calls to family, family contacts, and directory assistance. Incentive gift certificates will be provided: \$50 for completing assessments at each of the baseline and 6-month follow-ups, and \$75 at 12- and 18-month follow-up. The UMMS Project Director, [name] will oversee retention at both sites.

6.2.3. Blinding: All study staff except the Research Assistant, and Project Director Database Manager ([name]) will be blinded. Blinding the Research Assistant, Project Director, and Database Manager would be impractical given that they will be randomizing the patients to the intervention groups, or tracking the randomization process. The impact of un-blinding the Research Assistant, the Project Director and the database manager will be minimal because evaluation surveys are completed directly by participants, and they will NOT perform any data entry or statistical analysis. The pulmonary lab technicians (for outcomes measurement) will be blinded, as well as the PIs, study statistician, and all study investigators and those involved with randomization codes. These un-blinded staff will have no access to the data, no influence on the outcome assessments, and no involvement in data analysis. Staff delivering the interventions and preparing reports for the independent monitoring will not be blinded.

The study arms will be coded and referred as non-informative A vs. B, but not intervention vs. control, or a coding revealing the nature of intervention arms. The non-informative coding/naming of intervention arms will be kept until the planned main outcomes analysis is completed. Unblinded project staff are prohibited to reveal the information on the coding of study arms to anyone.

The blind will be broken in the case of a serious adverse event. In this event, Drs. [name] and [name], the study pulmonary physicians, will break the blind in order to address the SAE.

The data and safety monitoring board (DSMB) will also be blinded unless the unblinding is needed to investigate severe adverse events or other patient safety issues, required by NCAAM, IRB or law.

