Since the measures are longitudinal, we will also use linear or generalized mixed models to evaluate the intervention effects on ACQ score and presence of symptoms. We will include intervention indicator (MBSR=1 and HLC control=0) in the mixed models to estimate intervention effect. To account for auto-correlations among repeated measures on the same patient, we will include in the mixed models patient level random effects and use either first order autoregressive correlation or unstructured covariance structure for robust estimates. Within physician correlations will be modeled by including physician level random effects. We will also consider inclusion of key physician attributes such as sub-specialty in the models in order to understand how physician factors may influence the intervention effects. Since interventions will be delivered by class, we will model each class as a potential random effect in the model and test if inclusion of the class level random effect improves model estimation. If class level random effect exists, we will fit a two level hierarchical model (repeated measures on patients nested within each class). We will estimate the intervention effects with and without adjusting for patient socio-demographic and clinical co-variables. Covariate adjustments will focus co-variables that are unbalanced between the two arms, or inclusion of them will lead to substantial reduction of

variance in estimates of intervention effects, or those modifying the intervention effects. To test whether intervention effects vary by these factors, we will test the significance of the interactions between intervention indicators and each co-variable. A significant interaction term signals potential variation of intervention effect, which warrants further investigation.

To model presence of any specific component of asthma control at follow-up time points, we will use mixed effects logistic regression models. This analysis is important to understanding whether specific control component worked well or not among patients, and if there is any differential effect between the two arms. To model intervention effects on number of symptoms at each follow-up, we will use mixed effects Poisson regression models. General modeling approaches are similar to those for ACQ scores and thus not repeated, except that the underlying statistical distributions differ.

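### The power calculation in Section 9.2 allows for clustering by physician, which does not inflate the arm contrast, and makes no allowance for clustering by class, which does; power is not thereby shown to be overstated

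*Combined protocol and SAP*

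**What the plan says.** Section 9.2 claims that a 0.25-point ACQ difference can be detected "at 5% significance level and at least 80% power" with 108 analysed patients per arm. The assumed SD is 0.66, with means described as averaged over three follow-up visits, and the serial correlation within patients is 0.45. The only clustering named is by physician: "We expect to recruit patients from 12 physicians at each site, with on average each physician contributing 9 patients", and "we conservatively assumed a modest within physician correlation of 0.05". No class ICC, class size or class design effect is given.

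Sections 4.3 and 6.2.2 randomise individual patients within site and severity strata. They also say that each cohort is randomised together and sent to common MBSR and HLC classes.

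Section 9.6 plans for both kinds of clustering. On physicians: "Within physician correlations will be modeled by including physician level random effects". On classes: "Since interventions will be delivered by class, we will model each class as a potential random effect in the model". The class effect is kept only if a test shows that it improves the model; the physician effect carries no such condition.

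**The concern.** A cluster effect inflates the variance of a treatment contrast when the cluster lies wholly within one arm. Physician is crossed with arm here, because a physician's patients are allocated one by one. Class is nested in arm, because an MBSR class contains no HLC patients. Section 9.2 therefore allows for the component that does not matter to the contrast and leaves out the one that does.

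Two things are at stake. The power section and the analysis section assume different cluster structures, so a reader cannot tell how large a class ICC the trial can tolerate. The same imbalance also carries into the analysis: the physician effect is definite, while the class effect depends on a test that will have little power with four or five study patients per class. If that test drops a real class effect, the standard error of the main comparison is too small.

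**Working it through.** **Inputs.** From 9.2: 108 per arm, difference 0.25, SD 0.66, serial correlation 0.45, 5% level, 24 physicians × 9 = 216. Recruitment: "In total, the study will recruit 254 participants, 127 from each of the sites". Retention: "We expect to retain 85% of participants at 18-months" (254 × 0.85 = 215.9). Sections 3 and 4.3 give 13 cohorts. Assumed here: a two-sided test, the same 0.45 between any two visits including baseline, and a class ICC of 0.02 to 0.15.

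**Formula.** SE = 0.66 × √(f × DE × 2/108); power = Φ(0.25/SE − 1.96). DE is the design effect and f is the variance factor after baseline adjustment. Section 9.2 does not settle what the 0.66 refers to, so three readings are carried:

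- SD of the three-visit mean. The mean of three visits has relative variance (1 + 2 × 0.45)/3 = 0.633, so its correlation with baseline is 0.45/√0.633 = 0.565, and f = 1 − 0.565² = 0.680.
- Per-visit SD, three visits averaged: f = 0.633 − 0.45² = 0.431.
- 18-month visit alone: f = 1 − 0.45² = 0.7975.

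**The plan's own figure.** The implied physician design effect is 1 + (9 − 1) × 0.05 = 1.40. On the first reading, SE = 0.66 × √(0.680 × 1.40 × 2/108) = 0.0877 and power = Φ(2.852 − 1.96) = 81%. The requirement for 80% is 105 per arm, close to the 108 used. The stated figure reproduces.

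**Does physician clustering inflate the contrast?** A simulation of 24 physicians × 9 patients, ICC 0.05, individual allocation within site and 20,000 runs gave a variance ratio of 0.99 against independence, not 1.40. Physician is not a stratum, so the cancellation holds on average rather than exactly.

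**Does class clustering inflate it?** Taking 13 cohorts per site and one class per arm per cohort gives 26 classes per arm: 108/26 = 4.15 study patients per class if only analysed patients count, or 127/26 = 4.88 if all recruited patients do. The design effect is 1 + (m − 1) × ICC, which is 1.16 at m = 4.15 and ICC 0.05. The same simulation gave 1.15.

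**Power at 108 per arm** (ranges run over m = 4.15 to 4.88):

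| Clustering allowed for | DE | Three-visit-mean SD | Per-visit SD | 18 months alone |
|---|---|---|---|---|
| None | 1.00 | 92% | 99% | 88% |
| Physician, ICC 0.05 | 1.40 | 81% | 95% | 75% |
| Class, ICC 0.02 | 1.06-1.08 | about 90% | 98% | 85-86% |
| Class, ICC 0.05 | 1.16-1.19 | 87-88% | 97-98% | 81-83% |
| Class, ICC 0.10 | 1.32-1.39 | 82-84% | 95-96% | 75-78% |
| Class, ICC 0.15 | 1.47-1.58 | 76-79% | 92-94% | 70-73% |

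**Crossover.** The class design effect reaches 1.40 at ICC 0.40/3.15 = 0.127 or 0.40/3.88 = 0.103. On the first reading, 80% power tolerates a design effect of 1.451, that is, a class ICC of 0.451/3.15 = 0.143 or 0.451/3.88 = 0.116.

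**Larger classes.** If the two sites' patients were counted in shared classes, m = 108/13 = 8.31. On the first reading, power is then 82% at ICC 0.05 (DE 1.37) and 73% at 0.10 (DE 1.73).

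**The case against.** The strongest reply is that the physician allowance, though attached to the wrong cluster, does the job. With classes this small, 1.40 exceeds the class design effect until the class ICC passes about 0.10 to 0.13, so exchanging the terms raises the calculated power over most of the plausible range. That stands.

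A reader might infer that the trial is underpowered, or that the plan's inputs miss their own 80% target. The second inference arises if 0.45 is used directly as the correlation of baseline with the three-visit mean, which gives 75%. But 9.2 presents 0.45 as a correlation between measurements on the same patient. The matching correlation with a three-visit mean is 0.565, and the result is 81%. The 75% belongs to the 18-month visit alone. The documents do not support a claim that power is overstated.

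It is also fair to say that the 1.40 is implied by 9.2 and not printed there. A plain two-sample calculation with no baseline adjustment and no clustering gives 79.5% at 108 per arm, so the figure may contain no design effect at all. In that case a class ICC of 0.05 would take that calculation to about 72-73%.

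The class size is derived as well. Ten to eleven patients per cohort over 13 cohorts is 130 to 143, which fits 127 per site and not 254 overall. The two scheduling options in 5.1 could make classes smaller still.

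Finally, a physician random effect does no harm to the arm contrast, so there is no reason to remove it from 9.6.

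**Conclusion.** The point holds as a fault in the basis of the power figure. Section 9.2 inflates for a factor crossed with arm, calls this conservative, and gives no allowance for the factor nested in arm that 9.6 itself identifies.

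On the reading that reproduces the plan's figure with its clustering term, power with a class term stays above 80% up to a class ICC of about 0.12 to 0.14. That limit falls to about 0.08 to 0.10 if baseline adjustment does not reduce the class variance. On the per-visit reading power is 92% or more throughout. For 18 months alone, the time point named in the primary hypothesis, it falls below 80% above a class ICC of about 0.06 to 0.075. These results rest on an assumed class ICC, a derived class size, a two-sided test and equal correlation between visits.

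**What to change.** In 9.2, replace the physician allowance with a class allowance. State the assumed number of study patients per class and whether 0.66 is a per-visit or a three-visit-mean SD. Show power over class ICC 0.02 to 0.15, and remove the claim that the physician correlation makes the calculation conservative.

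In 9.6, keep the class random effect in the main ACQ model whatever its test shows. The physician random effect can stay as planned. Do not change the sample size.

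The cost is one recalculated paragraph and one amended sentence. Standard errors will be slightly wider when the class effect is small, and the stated power may fall below 80% at the upper end of the class ICC range.

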9.3 Definition of Populations

We will follow the intent-to-treat principle in the primary analysis. Study arm status of patients will be coded as randomized at enrollment, and the data will also be analyzed per protocol (versus actual interventions received). We will avoid potential switch of patients between arms. We anticipate the potential switch of study arms per patient is minimal to know. For missing data (e.g., missing visits or dropouts prior study completion), we propose to use multiple imputation methods that have become the standard approach in clinical trial studies and we routinely apply using Stata MP 13 (Stata Corp., College Station, TX).

9.4 Interim Analyses and Stopping Rules

This is a fixed size RCT and no interim analysis will be conducted. Our success in meeting recruitment goals, the excellent follow-up response rate, and the effectiveness of the quality controls, and the fact that no

adverse events were reported in the pilot trial of this intervention make the necessity of stopping the present trial for these reasons a remote one.

9.5 Outcomes

9.5.1 Primary Outcome: The primary objective is to evaluate the effect of MBSR in improving asthma control as assessed by the Asthma Control Questionnaire. *Hypothesis: Asthma control as assessed by the Asthma Control Questionnaire³ will improve significantly more in MBSR than in HLC participants at 18 month follow-up.*

9.5.2 Secondary Outcomes:

1) Asthma-related QoL. *Hypothesis: Asthma-related QoL (AQoL)⁴ will improve more in MBSR than HLC participants from baseline to 18-month follow-up.*

2) Respiratory interoceptive accuracy and its mediating effect on asthma control, QoL, and medication use. *Hypotheses: MBSR will result in improved accuracy (Breath Perception Discrimination Test) at 6-, 12- and 18-months compared with HLC, and will be correlated with improved asthma control, QoL, and medication use.*

3) Lung function (change from baseline in 2-week average morning peak expiratory flow (PEF) and spirometry (Forced Expiratory Volume in 1 second (FEV₁)) at 6-, 12- and 18-months compared with HLC. *Hypotheses: There will be no deterioration, and possibly improvement, in lung function in MBSR participants from baseline to 6-, 12- and 18-months as measured by PEF and FEV₁ as compared with HLC.*

4) Cost-effectiveness in asthma control and management. *Hypothesis: MBSR will be associated with improved cost-effectiveness and improved cost-utility by 18 months as compared with HLC. This will be based on clinical outcomes (e.g., asthma control, QoL, medication use) as well as quality-adjusted life years.*

To conduct cost analysis, we will collect data on number of moderate and severe exacerbations, asthma-related regularly scheduled office visits, acute care visits, hospitalizations, emergency room visits, need for intubation or mechanical ventilation, and other costs during the prior 6 months at baseline, 6-, 12- and 18-month follow-up and associated clinic and hospital costs. The cost data will be determined by two methods: Self-report and actual hospital and health system costs (direct and indirect) obtained from administrative reimbursement data (see Letters of Support from fiscal offices). Brief Treatment Cost Analysis Tool (TCAT), a validated costing tool for counseling interventions,⁸⁹ will be used to calculate cost of delivering MBSR and HLC.

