Secondary Outcomes: Analytic approaches for asthma-related QoL, respiratory interoceptive accuracy, lung function are generally similar to those for the two primary outcomes. To test the mediation effect of respiratory interoceptive accuracy (RIA) on asthma control, QoL, and medication use, we will first compare the difference in RIA by treatment arm. We will then use difference-to-difference approach to analyze the longitudinal associations of the changes in RIA from baseline to each follow-up time point with changes in ACQ, QoL and medication use from baseline to comparable follow-up time points.¹⁰¹⁻¹⁰³ Since we will have measures on three follow-ups, we will use linear mixed models where ACQ, QoL and medication use are treated as outcomes, RIA as the primary predictor, with and without an interaction term between RIA and MBSR indicator. These analyses will help answer whether MBSR intervention improved RIA, and whether between treatment differences in RIA would explain the observed differences in ACQ, QoL and medication use. We will compute incremental cost-effectiveness of MBSR compared with HLC as the difference in average health care costs per study participant over 18 months between MBSR and HLC, divided by the difference in average ACQ. As planned for another NIH-funded cost-effectiveness study (5R01AA009892-19), we will use the overlap between self-reported and administrative reimbursement data to estimate models of administratively estimated inpatient, outpatient, and medication services data as functions of the self-reported data. We will apply these models to all self-reported data to derive the 18-month health care costs of MBSR and HLC. We will calculate the cost of delivering the MBSR and HLC from the Brief Treatment Cost Analysis Tool (TCAT), a validated costing tool for counseling interventions.⁸⁹ Sensitivity analysis: ICER ratios will be computed between baseline and active comparator, with usual considerations of uncertainty evaluated in a probabilistic sensitivity analysis to determine the level to which our cost-effectiveness conclusions are robust.

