To compare the cost-effectiveness in asthma control and management between the comparator arms we will compute per-person incremental total cost per defined measure of additional clinical benefit. More specifically, total costs will include direct and indirect costs of intervention, and per-person overall healthcare/hospital care costs over the entire follow-up period to study completion. Key clinical endpoints will include prevention of exacerbations, unscheduled acute care office visits, and emergency room visits, as well as additional quality of life achieved. We will use general linear models to analyze the associations of the person-level intervention cost with ACQ scores, and use the model to predict per-arm required intervention effects. Secondly, we will use linear models to analyze the associations of person-level intervention cost with total healthcare/hospital care cost, and examine whether increases in intervention cost are correlated with lower average healthcare/hospital care cost. This "return-on-investment" analysis will provide information on monetary savings on care cost per dollar of MBSR intervention. Following these steps, we will apply log-linear models to analyzing the intervention-to-care cost ratios, and examine whether they differ by MBSR/HLC status, and other patient/physician factors.

Missing data: For most longitudinal trial studies, missing data and dropouts are unavoidable. To account for potentially differential/informative dropouts, we will apply inverse probability weighting methods that [name] developed for clinical trial studies with [name] and associates.^{104 #2421, 105} This method first estimates the probability of dropout/lost-to-follow-up of a participant based on his/her sociodemographic and health profiles, and uses the estimated probabilities as weights in the regression analysis. This method effectively removes

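### Secondary objective 4 promises QALY-based cost-utility with no specified way to obtain it, and Section 9.6 gives two unreconciled cost numerators for its cost-effectiveness ratios

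*Combined protocol and SAP*

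**What the plan says.** **The promise.** Sections 1.2 and 9.5.2 hypothesise that MBSR will improve both cost-effectiveness and cost-utility by 18 months compared with HLC. On the basis for this, 9.5.2 states: "This will be based on clinical outcomes (e.g., asthma control, QoL, medication use) as well as quality-adjusted life years"; Section 1.2 says the same. Section 9.1 also lists cost-utility among the secondary objectives, without mentioning QALYs.

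**The measures.** The only quality-of-life instrument in the Section 6.2 table is the AQoL. It has 32 items scored 1 to 7, and the overall score is the average of four domain scores.

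**The first ratio.** The Secondary Outcomes paragraph of Section 9.6 defines incremental cost-effectiveness as "the difference in average health care costs per study participant over 18 months between MBSR and HLC, divided by the difference in average ACQ". To obtain the health care costs, the analysts will "estimate models of administratively estimated inpatient, outpatient, and medication services data as functions of the self-reported data", and then: "We will apply these models to all self-reported data to derive the 18-month health care costs of MBSR and HLC". The following sentence says that programme delivery cost will be calculated with the TCAT tool. It does not say where that cost enters.

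**The second ratio.** The next paragraph of 9.6 plans an incremental total cost per unit of clinical benefit. There, "total costs will include direct and indirect costs of intervention, and per-person overall healthcare/hospital care costs" over the whole follow-up. The key endpoints named are "prevention of exacerbations, unscheduled acute care office visits, and emergency room visits, as well as additional quality of life achieved".

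**The concern.** There are two separate matters.

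First, a hypothesis stated in two places has no specified analysis behind it. If the utility derivation is left open, any choice made after the data are seen is post hoc, and the cost-utility claim could not be presented as pre-specified.

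Second, the cost per ACQ point uses the trial's primary measure, and an analyst who follows its definition to the letter would leave out the cost of the programme under evaluation. Such a ratio can show a saving where total cost shows none. If care costs do not differ between arms, it gives zero cost per ACQ point whatever MBSR costs to deliver. An analyst who instead carries the later definition of total cost across to the ACQ ratio gets a different answer from the same data. The plan does not say which is meant.

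**Working it through.** **Check 1: is there a route to a QALY?** The documents state no QALY, utility or ICER figure, so there is nothing to reproduce. The check is a count and a reading.

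The Section 6.2 table has 18 rows:

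- primary outcome (1): ACQ;
- secondary endpoints (9): symptom diary, medication use, AQoL, respiratory interoceptive accuracy, exacerbations and utilisation/cost, spirometry, PEF, mindfulness, perceived stress;
- moderating and process variables (8): sociodemographics, medical and psychiatric history, adherence, fidelity, days missed, triggers, confounding effects, CAM use.

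The total is 1 + 9 + 8 = 18. Rows described as a preference-based utility measure: 0.

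A utility could also come from a mapping. The AQoL row gives an averaged 1–7 score and no mapping, and 9.6 names none. The nearest item in 9.6 is the last endpoint in the second ratio, additional quality of life, and it is not tied to a utility or to time. The chain from measure to utility to QALY to cost per QALY therefore has no specified link.

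**Check 2: what would the written ACQ ratio miss?** Define:

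- S = health care saving with MBSR (HLC minus MBSR);
- D = delivery-cost difference (MBSR minus HLC);
- E = ACQ benefit of MBSR, taken as positive here only to fix the algebra.

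Then:

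- ratio as written (health care costs only) = −S/E;
- ratio with total cost = (−S + D)/E;
- gap = D/E.

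The planned effect in Section 9.2 is E = 1.49 − 1.24 = 0.25, so the gap is D/0.25 = 4D per ACQ point. At the 0.5 change that Section 6.2 calls important, it is D/0.5 = 2D.

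The documents give no costs. The values of D below are assumptions that show scale only:

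| Assumed D (dollars) | Gap at E = 0.25 | Gap at E = 0.5 |
|---|---|---|
| −100 | −400 | −200 |
| 0 | 0 | 0 |
| 100 | 400 | 200 |
| 400 | 1,600 | 800 |

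When there is a care saving (S > 0), the true total-cost saving as a share of the saving shown is (S − D)/S = 1 − D/S. For assumed D/S:

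| D/S | Total-cost saving ÷ saving shown |
|---|---|
| −0.5 | 1.5 |
| 0 | 1 (no error) |
| 0.5 | 0.5 |
| 1 | 0 |
| 2 | −1 (a net cost as large as the saving shown) |

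The sign reverses when D exceeds S, and E cancels from that condition. With S = 0, the written ratio is 0 for any D.

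**Check 3: could delivery cost already sit inside health care costs?** Not on the text. Those costs are modelled from inpatient, outpatient and medication services. The second-ratio paragraph also treats the two as distinct: it will "examine whether increases in intervention cost are correlated with lower average healthcare/hospital care cost", and it adds them to form total cost.

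**The case against.** The strongest reply concerns the second matter. The paragraph with the ACQ ratio runs in order from ratio, to health care cost, to TCAT delivery cost, to sensitivity analysis of the ICERs. That order suggests delivery cost was meant as an input, since the paragraph gives it no other use. The next paragraph defines total cost to include intervention cost and is introduced as comparing the arms on asthma control and management, which is what the ACQ measures. Its endpoint list is worded as non-exhaustive, so ACQ is not excluded. The same paragraph also plans models relating person-level intervention cost to ACQ scores.

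Much of this stands. A reader might infer that 9.6 leaves delivery cost out of the economic evaluation altogether. The documents do not support that: the cost is calculated, and one of the two ratios includes it. What remains is that the only explicit definition of cost per ACQ point uses health care costs alone. Nothing says that total cost replaces it, and a regression of ACQ on intervention cost is not a total-cost ratio.

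Size is also fairly contested. Only the between-arm difference in delivery cost matters, and Section 5.1 describes HLC as matched to MBSR in schedule and structure, so D may be close to zero. It cannot be taken as exactly zero. Section 5.1 gives MBSR an all-day class and describes HLC without one, although 5.2 and 5.3.2 read as if both programmes have it. Section 4.3 adds an orientation session for MBSR.

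On the first matter, a reader might infer that QALYs cannot be obtained from this trial at all. That goes too far. Whether a valid derivation from the collected data exists cannot be judged from these documents; they show only that none is specified. Nor does the précis show a plan limited to cost-effectiveness. It uses the same heading under which 1.2 and 9.5.2 list cost-utility, and omits the hypothesis text.

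**Conclusion.** The QALY point holds in full: 0 of 18 table rows supply a utility, and 9.6 contains no mapping, QALY calculation or cost-per-QALY ratio. As written, the plan cannot deliver that part of objective 4. This rests on the public text, from which the title material and Section 12 (Committees) are absent; neither is a likely place for such a specification.

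The numerator point holds as an inconsistency, not as an established omission across 9.6. On the literal reading, the cost per ACQ point is off by D/E, or 4D at the planned effect. The actual amount is unknown and may be near zero. A reader might infer that the trial will report a false saving; without any cost figures the documents do not support that, and the total-cost ratio would expose a net cost if both ratios are reported.

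Both matters concern a secondary objective, and the primary outcome is unaffected. They should be corrected because the text otherwise promises a result it cannot produce and allows two answers to one question.

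**What to change.** 1. **Cost-utility.** Remove the cost-utility and QALY claim from Sections 1.2, 9.1 and 9.5.2. Alternatively, state in 9.6 a valid utility derivation from data already collected, with the QALY calculation and the cost-per-QALY ratio, and fix it before the arm codes (Section 6.2.3) are revealed. If no valid derivation can be named by then, the claim should go.
2. **Numerator.** In 9.6, define one incremental cost: health care cost plus TCAT delivery cost, MBSR minus HLC. Use it as the numerator of every ICER, including cost per ACQ point. A ratio of health care cost alone may still be reported if it is labelled as such.

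The cost is wording in four sections. No new data, visits or questionnaires are needed, because health care costs and TCAT delivery costs are already planned (Sections 6.2, 9.5.2 and 9.6). As a protocol modification it needs approval from both IRBs (Section 11.1) and passes through the funder's programme-officer approval (Section 10.3.5).
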